6.3 PATIENT SETS ANALYSED

Treated set:

This patient set includes all patients who were dispensed trial medication and were documented to have taken at least one dose of investigational treatment. The treated set is to be used for all planned analysis.

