##### **4.1.4.1.1 Dose escalation scheme for BIBW**

Initially, 3 evaluable patients will be treated per dose level. As soon as one patient experiences a DLT (see section 5.2.3), 3 new patients will be treated at that dose level, to treat a minimum of 6 evaluable patients. If no other patients experience DLT the dose will be escalated to the next level and 3 further patients treated. If two or more of six patients

experience DLT, three additional patients will be treated at one dose tier below unless six have already been treated at that dose tier.

The MTD (see section 5.2.4) is the highest dose at which no more than one of 6 patients experiences DLT. Once the MTD is determined, patient enrolment at higher dose tiers will be suspended.

The MTD cohort in each Regimen may be expanded to include up to 12 patients.

Intra-patient dose escalation will not be permitted.

The first three patients at each dose level will be treated and observed for at least 6 weeks (42 days) during RT before the next cohort of new patients are treated at the next higher dose level (Table 4.1.4.1.1: 2 and 4.1.4.1.1: 3).

Table 4.1.4.1.1: 1 Rules for dose escalation for regimen M and U

Number of Patients with DLT at a Given Dose Level	Escalation Decision Rule
0 out of 3	Enter 3 patients at the next dose level.
1 out of 3	Enter at least 3 more patients at this dose level. - If 0 of these 3 patients experience DLT, proceed to the next dose level. - If 1 or more of this group suffer DLT, then dose escalation is stopped. Three (3) additional patients will be entered at the next lower dose level if only 3 patients were treated previously at that dose.
$\geq 2$ out of 3	Dose escalation will be stopped. Three (3) additional patients will be entered at the next lower dose level if only 3 patients were treated previously at that dose.

The decision regarding dose escalation steps will only be made after agreement with the sponsor's Trial Clinical Monitor (TCM).

Dose escalation and entry of patients into the next dose cohort will begin only after accrual of the required minimum number of patients has been achieved and all patients in the cohort are considered following completion of 6 weeks BIBW2992 treatment ((42 days ) during RT). Patients who are not treated until the end of these 6 weeks for any reasons other than DLT will be replaced (section 6.3.1).

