#### **4.2.3 Management of expected adverse events**

##### Management of diarrhoea

Close monitoring and proactive management of diarrhoea is essential for successful treatment of patients with BIBW 2992 and/or TMZ. Early and appropriate intervention can prevent the development of more severe diarrhoea. In most cases, loperamide controls diarrhoea caused by BIBW 2992 and/or TMZ.

Loperamide should be available at the start of therapy and kept with the patient at all times; it is therefore advisable that patients be given a prescription at the time of initiating study treatment.

The recommendations for management are as follows:

- If any diarrhoea is experienced (CTCAE Grade 1), two 2 mg loperamide tablets should be taken immediately, followed by one 2 mg tablet with every loose bowel movement, up to a maximum daily dose of 10 tablets (20 mg).
- Patients should be advised to avoid lactose-containing products or any foods known to aggravate diarrhoea.
- Oral hydration is essential regardless of severity; appropriate rehydration (1.5 litres/m^2/day plus equivalent of actual fluid loss) has to be ensured in the event of CTCAE Grade 2 and Grade 3 adverse reaction.
- For CTCAE Grade 3 diarrhoea lasting  $\geq 2$  days or CTCAE Grade 2 diarrhoea lasting  $\geq 5$  days despite adequate antidiarrhoeal treatment, BIBW 2992 and/or TMZ must be paused until recovery to CTCAE  $\leq$  Grade 1 or baseline in the individual treatment course. Upon recovery, BIBW 2992 and/or TMZ should be resumed at a reduced dose according to the dose reduction scheme outlined in Section 4.1.4.

The occurrence of diarrhoea and the outcome of treatment will be recorded in the AE section of the eCRF. Antidiarrhoeal treatments should be documented in the concomitant medication section of the eCRF.

If despite optimal supportive care and the treatment pause, diarrhoea does not resolve to CTCAE Grade  $\leq 1$  or baseline within 14 days, the patient must be removed from the study. Exception to this in patients who derive obvious clinical benefit according to the investigator's judgment could be considered upon discussion with BI's Clinical Monitor Local (CML).

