### **6.3.1 Replacement of patients**

Patients who do not receive study treatment during the chemoradiation phase for more than 5 consecutive days or more than 8 non-consecutive days for any reasons other than DLT will be replaced.

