### **7.3 PLANNED ANALYSES**

All patients who receive at least one administration of a study treatment regimen will be included in the analysis of efficacy and safety. Results will be presented by treatment regimen and dosage cohort but comparisons will not be carried out between regimens or cohorts.

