## **7.3.4 Interim analyses**

No formal interim analysis of efficacy is planned.

A safety analysis may be performed after the last patient remaining in the last dose cohort of each treatment regimen (Regimen M and Regimen U) has completed the concomitant treatment period (6 weeks of concomitant radiochemotherapy) or has dropped out of the study. A database snapshot will be performed for this purpose. Objectives of this analysis will be:

- To determine the MTD for each regimen (Regimen M and Regimen U);
- To recommend the optimal dose of BIBW 2992 to investigate in future studies.

This analysis will therefore summarise incidence of DLT, for MTD determination. The analysis will also report safety observations collected beyond the concomitant treatment period where feasible, to facilitate selection of the optimal dose. Additional details of this

safety analysis will be specified in the Trial Statistical Analysis Plan (TSAP) and the results will be documented and archived.

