7. PLANNED ANALYSIS

For end of text tables, unless otherwise specified, the set of summary statistics is: N, mean, standard deviation (SD), minimum, median and maximum.

Tabulations of frequencies for categorical data will include all possible categories and will display the number of observations in a category as well as the percentage (%) relative to the respective treatment group. Percentages will be given in whole numbers. The category missing will be displayed only if there are actually missing values. Unless otherwise specified, percentages will be based on all patients in the respective patient set whether they have non-missing values or not.

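### The DLT summary meant to determine the MTD counts all treated patients although escalation counts evaluable ones, and the DLT window ends at 60 Gy in one place and at 42 days in two others

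*SAP*

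**What the plan says.** **Analysis set.** SAP 6.3 defines only the treated set (at least one documented dose) and states: "The treated set is to be used for all planned analysis". SAP 7 adds: "Unless otherwise specified, percentages will be based on all patients in the respective patient set whether they have non-missing values or not". SAP 7.4, which aims the DLT summary at determining the MTD, makes no exception. Protocol 7.3 is similar: "All patients who receive at least one administration of a study treatment regimen will be included in the analysis of efficacy and safety". Protocol 7.3.4, on the optional safety snapshot, says: "This analysis will therefore summarise incidence of DLT, for MTD determination".

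**Escalation.** Protocol 4.1.4.1.1 works with evaluable patients: three at first and, after one DLT, three more so as "to treat a minimum of 6 evaluable patients". It continues: "Patients who are not treated until the end of these 6 weeks for any reasons other than DLT will be replaced", and refers to Section 6.3.1. That section replaces patients who go without study treatment in the chemoradiation phase for "more than 5 consecutive days or more than 8 non-consecutive days for any reasons other than DLT will be replaced".

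**MTD limit.** Protocol 5.2.4 allows at most one patient in six with a DLT, which it also gives as 17%.

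**DLT window.** Protocol 4.1.4.1.1 lets missed radiotherapy fractions be made up after Day 42 and has DLTs assessed until the full 60 Gy has been given. Protocol 5.2.4 counts DLTs in the 42-day radiotherapy period and examines separately those arising once maintenance has started. SAP 5.1 defines the primary endpoint by onset in a 42-day concomitant period. SAP 7.4 puts DLTs with later onset in a separate listing.

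**The concern.** Two parts of the primary analysis do not match the rule that drives the trial.

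The first is the denominator. A patient who stops or pauses for a non-DLT reason is replaced and drops out of the cohort decision, but remains in the treated set. The reason need not be administrative. Under the diarrhoea guidance in Protocol 4.2.3, for Grade 2 diarrhoea lasting at least 5 days despite treatment, "BIBW 2992 and/or TMZ must be paused until recovery to CTCAE" Grade 1 or lower, or baseline. The diarrhoea criterion for a DLT in Protocol 5.2.3 starts at Grade 3. A pause of this kind longer than 5 consecutive days leads to replacement without a DLT. Patients who tolerated the drug poorly, but not badly enough for a DLT, would then lower the reported DLT rate, and the planned DLT summary would not show why.

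The second is the window. A DLT that begins after Day 42 while radiotherapy is still running can stop escalation under 4.1.4.1.1 and yet fall outside the SAP primary endpoint. The report could then show a primary DLT count that does not support the MTD it declares.

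**Working it through.** **The plan's own figure.** 1/6 = 16.7%, which rounds to the 17% in Protocol 5.2.4.

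**Denominator.** Inputs: 6 evaluable patients in a full cohort (Protocol 4.1.4.1.1) or 12 in an expanded MTD cohort (Protocol 4.1.4.1.1 and 7.6). Let k be the number of treated patients in that cohort who were replaced without a DLT. The documents give no value for k, so it is varied.

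Reported rate = DLTs / (evaluable patients + k)

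| k | 1 DLT, 6 evaluable | 2 DLTs, 6 evaluable | 3 DLTs, 12 evaluable |
|---|---|---|---|
| 0 | 1/6 = 16.7% | 2/6 = 33.3% | 3/12 = 25.0% |
| 1 | 1/7 = 14.3% | 2/7 = 28.6% | 3/13 = 23.1% |
| 2 | 1/8 = 12.5% | 2/8 = 25.0% | 3/14 = 21.4% |
| 3 | 1/9 = 11.1% | 2/9 = 22.2% | 3/15 = 20.0% |
| 6 | 1/12 = 8.3% | 2/12 = 16.7% | 3/18 = 16.7% |

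Dilution alone brings 2/6 or 3/12 down to 1/6 only when six patients in one cohort are replaced. A partly filled expansion cohort is more sensitive. With 11 evaluable patients and one replaced, two DLTs give 2/11 = 18.2% or 2/12 = 16.7%. In the whole-number percentages that SAP 7 prescribes these are 18% and 17%, on either side of the limit.

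**Window.** Inputs: 30 fractions, one per weekday, Monday to Friday (Protocol 4.2 and Appendix 10.6). Assumptions: Day 1 is the first fraction, and missed fractions are made up on the next available weekdays.

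- A Monday start has five full weeks (25 fractions, to Day 35) and five more weekdays, ending on Day 40.
- A Tuesday start has 4 fractions in its first week and 25 in the next five, which makes 29. The 30th falls on the following Monday, Day 42. Wednesday, Thursday and Friday starts also end on Day 42.

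| Fractions missed | Mon | Tue | Wed | Thu | Fri |
|---|---|---|---|---|---|
| 0 | 40 | 42 | 42 | 42 | 42 |
| 1 | 43 | 43 | 43 | 43 | 43 |
| 2 | 44 | 44 | 44 | 44 | 46 |

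With no missed fraction, radiotherapy ends by Day 42. With one, it ends on Day 43 whatever the starting weekday, and the two windows differ.

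Take six evaluable patients with one DLT by Day 42 and a second DLT, in another patient, starting on Day 43 before that patient's radiotherapy is complete. The 42-day window gives 1/6 = 17%, within the limit. The 60 Gy window gives 2/6 = 33%, above it.

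**Illustration with assumed risks (not in the documents).** The chance of at most one DLT in six patients is (1 − p)^6 + 6p(1 − p)^5, where p is the per-patient DLT risk in the window. Suppose every patient's window is extended and p rises by 5 percentage points.

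| p by Day 42 | p to 60 Gy | Chance of at most 1 in 6, 42 days | Chance of at most 1 in 6, 60 Gy |
|---|---|---|---|
| 15% | 20% | 0.78 | 0.66 |
| 20% | 25% | 0.66 | 0.53 |
| 30% | 35% | 0.42 | 0.32 |

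A 5-point rise is a generous assumption for a gap of a few days. The table shows direction and scale; it is not a forecast.

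**The case against.** **On the denominator.** The escalation rule is a count of patients with DLTs, so percentages on the treated set do not feed it. Protocol 7.3.1 asks for numbers as well as percentages by cohort, so the counts stay visible. The treated set follows Protocol 7.3. SAP Table 6.2: 1, item C3.1, flags patients who miss more than 8 afatinib doses in total or more than 5 in a row, nearly the limits in Protocol 6.3.1, so many replaced patients would be identified anyway. All of this is fair, and it is why the effect is an understated rate and not a wrong dose decision. But C3.1 counts only doses missed for reasons other than an adverse event. Replacement after a drug-related, non-DLT event, the informative case, is not caught by it, and no visible SAP text lists replaced patients.

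**On the window.** The 60 Gy sentence in Protocol 4.1.4.1.1 follows a sentence about delayed radiotherapy and can be read as the rule for that case. Protocol 5.2.4 and SAP 5.1 both tie the period to radiotherapy, so 42 days could be its nominal length. SAP item D2.1 checks for 60 Gy within the concomitant period, which suits a period that lasts until radiotherapy is complete. A definition in SAP Section 9, which is not in the public text, cannot be excluded. This reading is possible. Even so, 5.2.4 and SAP 5.1 both state 42 days without the exception, and D2.1 shows that the period is used in two senses within the SAP. Later DLTs would still appear in the separate listing and in the general DLT table of SAP 7.8.1, but outside the primary endpoint.

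**Conclusion.** The concern holds on both parts and should be fixed before the analysis.

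On the denominator, the planned summary can only report a rate equal to or below the one behind the cohort decision. The gap is 2 to 6 percentage points for 1/6 and 5 to 11 for 2/6 with one to three replaced patients. It does not normally change the MTD. The size depends on a replacement number that the documents do not give, and the effect is nil if nobody is replaced without a DLT.

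The window is the more consequential part per event. One missed fraction is enough to separate the two definitions, and one DLT in the gap moves a six-patient cohort across the MTD limit. How often that would happen is unknown: it needs both a radiotherapy delay and a DLT starting in a gap of a few days.

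**What to change.** 1. In SAP 6.3, define a DLT-evaluable set: patients with a DLT in the window, plus patients not replaced under Protocol 4.1.4.1.1 and 6.3.1. State which replacement wording it follows, because 4.1.4.1.1 speaks of not being treated to the end of the 6 weeks and 6.3.1 of a number of missed days.
2. In SAP 7.4, present the primary DLT summary by cohort on this set and beside it on the treated set. Keep the treated set for general safety tables.
3. List replaced patients by regimen and cohort with the reason, and mark those replaced after a drug-related adverse event that was not a DLT.
4. Reconcile Protocol 4.1.4.1.1, Protocol 5.2.4 and SAP 5.1 so that one DLT window serves both escalation and analysis. Use SAP item D2.1 in the same sense. Which window applies is for the sponsor to settle.

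The cost is SAP wording, one more table and one listing from data already collected, and a short protocol clarification. Two DLT rates side by side will need a sentence of explanation, and the evaluable-set rate may look less favourable.

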6.5 POOLING OF CENTRES

This section is not applicable because centre/country is not included in the statistical model.

6.6 HANDLING OF MISSING DATA AND OUTLIERS

PK parameters:

Missing data and outliers of PK data are handled according to BI standards. (2)

Time from first histological diagnosis:

If day of first histological diagnosis is missing it will be imputed using 15.

If both day and month of first histological diagnosis is missing they will be imputed using 1st July.

Adverse events:

Missing or incomplete AE dates are imputed according to BI standards. (4)

6.7 BASELINE, TIME WINDOWS AND CALCULATED VISITS

Baseline:

The measurement observed immediately preceding start of trial medication will be assigned to baseline; note that for some trial procedures (vital signs, mini mental state examination and laboratory tests) this may be the value measured on the same day trial medication was started.

7. PLANNED ANALYSIS

For end of text tables, unless otherwise specified, the set of summary statistics is: N, mean, standard deviation (SD), minimum, median and maximum.

Tabulations of frequencies for categorical data will include all possible categories and will display the number of observations in a category as well as the percentage (%) relative to the respective treatment group. Percentages will be given in whole numbers. The category missing will be displayed only if there are actually missing values. Unless otherwise specified, percentages will be based on all patients in the respective patient set whether they have non-missing values or not.

7.1 DEMOGRAPHIC AND OTHER BASELINE CHARACTERISTICS

Only descriptive statistics are planned for this section of the report.

7.2 CONCOMITANT DISEASES AND MEDICATION

Only descriptive statistics are planned for this section of the report.

7.3 TREATMENT COMPLIANCE

Only descriptive statistics are planned for this section of the report.

7.4 PRIMARY ENDPOINTS

DLT during concomitant treatment period:

The analysis of the primary endpoint will summarise DLT using descriptive statistics with the aim of determining the maximum tolerated dose (defined in Section 5.2.4 of the CTP) of:

- Afatinib in combination with TMZ when given concomitantly with RT (Regimen M);
- Afatinib when given concomitantly with RT (Regimen U).

An overall summary of AE occurrences with onset during the concomitant treatment period, which were defined to be DLTs by the investigator, will be presented. This will include the following AE attributes:

- Preferred term,
- Maximum CTCAE grade,
- Outcome,
- Time to first occurrence (relative to start of trial medication; see [Section 9.2](#) of this document).

Any AE meeting the criteria for DLT, regardless of date of onset, will be considered a significant adverse event (SIAE). The analysis of non-serious SIAEs and serious adverse events (SAEs) is described in [Section 7.8.1](#) of this document.

DLTs with onset after the concomitant treatment period will be listed separately.

7.5 SECONDARY ENDPOINTS

7.5.1 Key secondary endpoints

This section is not applicable as no key secondary endpoints have been specified in the CTP.

7.5.2 (Other) Secondary endpoints

Adverse events:

[figure not shown]
See Section 7.8.1 of this document.

Objective response:

Only descriptive statistics are planned for this section of the report.

PK parameters:

The analysis of standard PK parameters is performed according to BI standards. (2)

7.7 EXTENT OF EXPOSURE

Only descriptive statistics are planned for this section of the report.

7.8 SAFETY ANALYSIS

7.8.1 Adverse events

The analyses of AEs will be descriptive in nature. All analyses of AEs will be based on the number of patients with AEs (not the number of AEs). For this purpose, AE data will be combined in a 2-step procedure into AE records.

In a first step, AE occurrences, i.e. AE entries on the case report form, will be collapsed into AE episodes provided that all of the following applies:

- The same Medical Dictionary for Regulatory Activities (MedDRA) lowest level term was reported for the occurrences,
- The occurrences were time-overlapping or time-adjacent (time-adjacency of 2 occurrences is given if the second occurrence started on the same day or on the day after the end of the first occurrence),
- Treatment did not change between the onset of the occurrences or treatment changed between the onset of the occurrences, but no deterioration was observed for the later occurrence.

In a second step, AE episodes will be condensed into AE records provided that the episodes were reported with the same term on the respective MedDRA level and that the episodes are

assigned to the same treatment. For further details on summarisation of AE data, please refer to BI standards for AEs. (5)

CTCAE grade and investigator-defined DLT will be included as additional AE attributes. For the purposes of collapsing, additional deterioration rules will be defined for both attributes. In addition, in this trial, the standard AE attribute 'action taken with trial drug' is separated for afatinib and TMZ; the standard condensing rules will be applied for both.

The analysis of AEs will be based on the concept of treatment emergent adverse events. That means that all AEs occurring between first administration of trial medication until 28 days after last administration of trial medication will be assigned to trial medication. All AEs occurring before first administration of trial medication will be assigned to 'screening' and all AEs occurring after last administration of trial medication + 28 days will be assigned to 'post-study'.

Any AE meeting the criteria for DLT (defined in Section 5.2.2 of the CTP), regardless of date of onset, will be considered an SAE or SIAE.

According to ICH E3 (6), AEs classified as 'other significant' will include those non-serious and non-significant AEs:

- (i) with 'action taken = discontinuation' or 'action taken = reduced', or
- (ii) with marked haematological and other lab abnormalities or which lead to significant concomitant therapy as identified by the Trial Clinical Monitor/Investigator at a report planning meeting.

An overall summary of AEs will be presented, this will include the additional AE attributes maximum CTCAE grade and investigator defined DLT.

The frequency of patients with AEs will be summarised by treatment, primary system organ class (SOC) and preferred term (PT). Separate tables will be provided for patients with other significant AEs according to ICH E3 (5), for patients with non-serious SIAEs, for patients with SAEs, for patients with investigator defined DLTs and for patients with related AEs. An additional table will be produced of AEs stratified by the attribute maximum CTCAE grade.

The SOCs will be sorted according to the standard sort order specified by European Medicines Agency (EMA), PTs will be sorted by frequency (within SOC).

7.8.1.1 Adverse events of special interest

The following AEs are considered of special interest for this trial:

- Diarrhoea,
To be identified by the PT 'Diarrhoea';
- Nausea and vomiting,
To be identified by the PTs 'Nausea' and 'Vomiting';
- Rash and acne,
To be defined by the PTs contained within the project-defined special grouped-term category 'RASH/ACNE';

- Other AEs that occur with sufficient overall frequency,
To be determined by the trial team at the report planning meeting prior to database lock.

An overall summary of each of these AEs of special interest will be presented. This will include the additional AE attributes ‘Patients with investigator-defined DLTs’, ‘Maximum CTCAE grade’ and ‘Time to first occurrence’ (see [Section 9.2](#) of this document).

In addition, the frequency of patients with AEs will be summarised by treatment and project-defined special grouped-term category or preferred term. Where applicable, AE PTs will be re-categorised into one of the following grouped-term categories:

- Fatigue (FATIGUE);
- Nail effect (NAILS);
- Ocular effect (OCULAR);
- Rash and acne (RASH/ACNE);
- Stomatitis (STOMA).

Otherwise, AEs will be categorised according to MedDRA PT. Further tables will be provided for patients with related AEs for AEs stratified by the attribute maximum CTCAE grade.

The PTs identified within each of the project-defined special grouped-term categories will be listed.

